8.1 Potential Risks of Belatacept

8.1.1 Acute Rejection

Acute rejection is expected to be the principle risk in this study. In quantitative terms, the magnitude of renal function benefit necessary to offset the risk of incremental acute rejection (up to 10% based upon historical experience in the conversion setting) is not well characterized. Further, opinion among treating clinicians may vary based upon a number of factors, including individual patient needs and the clinician's assessment of the relative importance of rejection versus renal function as predictors of long-term outcomes. Thus, it is anticipated that a comprehensive review of the totality of safety and efficacy data will be necessary in order to characterize the clinical importance of acute rejection. The long-term data is reassuring since even patients that developed an episode of acute rejection had improved renal function when compared to CNI regimen at 5 years post-transplant.

8.1.2 Post-transplant Lymphoproliferative Disorder (PTLD)- **Black Box Warning**

WARNING:POST-TRANSPLANT LYMPHOPROLIFERATIVE DISORDER, OTHER MALIGNANCIES, AND SERIOUS INFECTIONS

See full prescribing information for complete boxed warning.

- **Increased risk for developing post-transplant lymphoproliferative disorder (PTLD), predominantly involving the central nervous system (CNS). Recipients without immunity to Epstein-Barr virus (EBV) are at a particularly increased risk; therefore, use in EBV seropositive patients only. Do not use NULOJIX in transplant recipients who are EBV seronegative or with unknown serostatus.**
- **Only physicians experienced in immunosuppressive therapy and management of kidney transplant patients should prescribe NULOJIX.**
- **Increased susceptibility to infection and the possible development of malignancies may result from immunosuppression.**
- **Use in liver transplant patients is not recommended due to an increased risk of graft loss and death.**

PTLD is a known complication of immunosuppression in renal transplant recipients. In the core

Belatacept studies in adults, the overall 3-year incidence rate of PTLD in Belatacept was consistent with published reports, the highest risk of PTLD with Belatacept was observed in EBV-negative subjects in whom a 13-fold increased risk of PTLD relative to EBV-positive patients was observed (9.9% in EBV-negative patients vs 0.7% in EBV-positive patients). Based upon these findings, Belatacept is contraindicated for use in patients with EBV serostatus negative or unknown. While there was also an increased risk in EBV-positive subjects with Belatacept compared to CsA within the studies, the absolute risk in this population was low. In addition to EBV-negative serostatus, CMV disease, and use of lymphocyte depleting therapy (LDT) for treatment of AR were also associated with an increased risk of PTLD in the core Belatacept studies. PTLD in Belatacept-treated patients was unusual in that a majority of cases presented in the CNS. The overall proportion of CNS PTLD in the Belatacept groups (MI and LI combined) was 9/14 (64%), which is higher than the proportion of CNS PTLD reported in the literature: 11% to 13% 32 PTLD should be considered in subjects who develop new neurologic signs or symptoms.

In the Phase 2 Belatacept conversion study, there were no cases of PTLD.

8.1.3 Malignancy

An increased incidence of malignancy is a recognized complication of immunosuppression in recipients of organ transplants. In the Phase 3 studies, overall malignancy rates were similar across all treatment groups, with the exception of PTLD.

In the Phase 2 Belatacept conversion study, the overall rates of malignancies were similar in patients converted to Belatacept and those who remained on CNI treatment.

8.1.4 Infection

Increased susceptibility to infection, including serious and fatal infections may result from the use of Belatacept, as with all immunosuppressive therapies. Overall incidences of infections, including serious fungal and viral infections, were similar across all therapies in the Phase 3 IM103008 and IM103027 studies. The most common serious infections across treatment groups were urinary tract infection (UTI) and cytomegalovirus (CMV) infections.

One (1) case of progressive multifocal leukoencephalopathy (PML) has been reported in the Belatacept renal transplantation program, in a subject receiving the MI regimen in study IM103027. PML should be considered in subjects who develop new neurologic signs or symptoms.

Tuberculosis (TB) has been more frequently reported in Belatacept-treated patients than CsA-treated patients. There were a total of 13 TB cases (12 with Belatacept and 1 with CsA) reported in the Phase 3 studies over 36 months. Nearly all cases of TB were reported in subjects who currently or previously resided in countries with a high prevalence of TB. It is recommended that all patients be screened for TB and treated for any evidence of latent disease prior to initiation of Belatacept therapy.

In the Phase 2 Belatacept conversion study, the overall rates of serious infections were similar in patients converted to Belatacept and those who remained on CNI treatment. The most common serious infections across treatment groups were urinary tract infection (UTI) and gastrointestinal infections. There were higher rates of adverse events due to non-serious viral and fungal infections in patients converted to Belatacept. There was one case of TB in a Belatacept-treated subject.

8.1.5 Other Potential Risks

Other potential risks include clinically relevant peri-infusion-related reactions, early post-transplant proteinuria, congestive heart failure or pulmonary edema, and autoimmune disorders. These events have been observed infrequently in Belatacept-treated subjects but are being closely monitored in all Belatacept clinical trials.

8.1.6 Non-investigational Product

Other medications used as support or escape medication for preventative, diagnostic, or therapeutic reasons, as components of the standard of care for a given diagnosis, may be considered as non-investigational products.

In this protocol, non-investigational product(s) is/are: Tacrolimus (TAC), Cyclosporine A (CsA), Mycophenolate Mofetil (MMF) or Mycophenolic Acid (MPA) and corticosteroids.

8.1.7 Description of the Dosage Form

Belatacept for Injection, 250 mg/Vial

Belatacept for Injection, 250 mg/Vial, is a sterile non-pyrogenic lyophilized powder. Each vial contains 275 mg of Belatacept, 550 mg of sucrose, 38.0 mg of sodium phosphate monobasic monohydrate, 6.4 mg of sodium chloride, and 1 N sodium hydroxide/1 N hydrochloric acid solution sufficient to adjust pH to 7.5. A 10% overfill is included in each vial to account for vial needle syringe (VNS) holdup.

8.1.8 Drug Product Preparation

Constitution and dilution of Belatacept for Injection 250 mg/Vial must be performed using silicone-free disposable syringes. Suitable fluids for constitution of the lyophile include sterile water for injection (SWFI), 0.9% sodium chloride injection (NS) or 5% dextrose injection (D5W). Prior to IV administration, the constituted solution is further diluted with NS or D5W to Belatacept concentrations between 2 mg/mL and 10 mg/mL. The infusion is to be administered through a sterile, non-pyrogenic, low protein binding in-line filter. Additionally, care must be taken to ensure the sterility of the prepared solution, as the drug product does not contain antimicrobial preservatives or bacteriostatic agents.

8.1.9 Constitution of the Lyophile

Each 250 mg vial of Belatacept for Injection should be constituted with 10.5 mL of a suitable constitution fluid (SWFI, NS or D5W) to provide a solution with a Belatacept concentration of approximately 25 mg/mL. Belatacept for injection, 250 mg/Vial, is not stored under vacuum. To avoid excessive foam formation in the vial, slowly inject the constitution fluid into the vial with the stream directed toward the vial wall and not into the lyophilized cake. The vial should be gently swirled and inverted until the lyophile dissolves. Although some foam may remain on the surface of the constituted solution, a sufficient excess of Belatacept is included in each vial to account for withdrawal losses, thus, 10.0 mL of a 25 mg/mL Belatacept solution can be withdrawn from each vial. Constituted solutions of Belatacept may foam, therefore, shaking should be avoided.

8.2.0 Preparation of the Infusion

Prior to IV administration, the constituted Belatacept solution (25 mg/mL) should be further diluted with either NS or D5W to final Belatacept concentrations ranging from 2 mg/mL to 10 mg/mL. Lyophiles constituted with SWFI may be further diluted with either NS or D5W. Lyophiles constituted with NS should be further diluted with NS and lyophiles constituted with D5W should be further diluted with D5W.

8.2.1 Handling and Dispensing

The product storage manager should ensure that the study drug is stored in accordance with the environmental conditions (temperature, light, and humidity) as determined by BMS. If concerns regarding the quality or appearance of the study drug arise, the study drug should not be dispensed and contact BMS immediately.

Investigational product documentation must be maintained that includes all processes required to ensure drug is accurately administered. This includes documentation of drug storage, administration and, as applicable, storage temperatures, reconstitution, and use of required processes (e.g. required diluents, administration sets).

8.2.2 Recommended Storage Conditions

Belatacept for Injection 250 mg/Vial should be stored refrigerated at 2° - 8° C (36°-46°F) and protected from long-term exposure to light. The reconstituted solution should be transferred from the vial to the infusion bag or bottle immediately. After further dilution with NS or D5W to Belatacept concentrations between 2 mg/mL and 10 mg/mL, the solutions may be stored in plastic, non-siliconized, IV bags or glass bottles. If not used immediately, the infusion solution may be stored under refrigerated conditions at 2° - 8° C (36°-46°F) and protected from light for up to 24 hours (a maximum of 4 hours

of the total 24 hours can be at room temperature: 20°C - 25°C [68°F-77°F] and room light). Regardless of storage condition, the Belatacept infusion must be completed within 24 hours of constitution of the lyophile.

8.2.3 Drug ordering and accountability (BMS will be shipping drug directly to study sites as needed)

8.2.3.1 Initial Orders

Following submission and approval of the required regulatory documents, a supply of Belatacept may be ordered from BMS by completing a Drug Request Form. (please see MOP) The first request may take place upon site activation.

Belatacept vials (40 mL) are shipped in quantities of five. The initial order should be limited to 25 vials (5 cartons of 5 vials each). Allow 5 business days for shipment of drug from BMS receipt of the Drug Request Form. Drug is protocol specific, but not patient specific. All drug product will be shipped by courier in a temperature-controlled container. Shipments will be made from BMS (There will be no weekend or holiday delivery of drugs).

It is possible that sites may have more than one Belatacept clinical study ongoing at the same time. It is imperative that only drug product designated for this protocol number be used for this study.

8.2.3.2 Re-Supply

Drug re-supply request form should be submitted electronically or by fax at least 5 business days before the expected delivery date. Deliveries will be made Tuesday through Friday. When assessing need for resupply, institutions should keep in mind the number of vials used per treatment dose, and that shipments may take 14 business days from [BMS or other third-party vendor] receipt of request. Drug is not patient specific. Be sure to check with your pharmacy regarding existing investigational stock to assure optimal use of drug on hand.

9. Study assessments and procedures [Please see: Schedule of Events (SOE) on page 19]:

9A. Belatacept Infusions

See SOE, on page 19, for complete Belatacept infusion schedule.

9A.1 Belatacept Infusion reactions**

In the event of new, serious, and unexpected toxicity potentially related to Belatacept, study drug administration should be interrupted. The investigator must immediately notify the medical monitor (MM). The subject will be considered eligible to receive further study drug treatment only after discussion with the medical monitor.

9B. Early Withdrawal of Study Drug Regimen – safety follow-up schedule:

Subjects in whom Belatacept dosing is discontinued should be placed on a conventional immunosuppressive regimen. To ensure the safety of immunosuppression conversion, repeated blood work for creatinine and drug levels will be performed a 1 week, 2 weeks and 4 weeks post-conversion. A safety follow-up clinic visit 1 month post-conversion will be scheduled.

9C. Study Stopping Rules

Subjects MUST discontinue investigational product (and non-investigational product at the discretion of the investigator) for any of the following reasons:

- Withdrawal of informed consent (subject's decision to withdraw for any reason)
- Any clinical adverse event (AE); abnormal laboratory test results such as refractory neutropenia after immunosuppression adjustment (absolute neutrophil count below 500), refractory life-threatening infection; occurrence of PTLD; refractory acute cellular rejection confirmed by kidney biopsy; or intercurrent illness which, in the opinion of the investigator, indicates that continued participation in the study is not in the best interest of the subject
- Pregnancy
- Loss of ability to freely provide consent through imprisonment or involuntary incarceration for

- treatment of either a psychiatric or physical (e.g., infectious disease) illness
- Missing 2 consecutive Belatacept infusions, unless the subject is receiving lymphocyte-depleting therapy or has approval by the medical monitor to remain in the study. Documentation will be required.
- Subjects receiving a maintenance dialysis regimen and deemed by the investigator to have functional graft loss and therefore do not require immunosuppression.

If PTLD or refractory rejection develops in two or more subjects of the study, the trial will be interrupted.

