7.5 LESS EFFECTIVE METHODS OF CONTRACEPTION

- Diaphragm with spermicide

- Cervical cap with spermicide
- Vaginal sponge
- Male Condom without spermicide
- Progestin only pills by WOCBP subject or male subject's WOCBP partner
- Female Condom*.

* A male and female condom must not be used together

8. Study Drug: Belatacept (Treatment with Belatacept will continue for 12 months)**:

Belatacept conversion dosing: 5 mg/kg IV on days 1, 15, 29, 43 and 57, followed by an infusion every 28 days thereafter. Calcineurin inhibitors (CNI) Taper: CNI dose will remain the same for week 1 and then will be tapered by 25% each week and discontinued at the end of week 4 (day 29).

Infusion pre-medications: none

Duration of Infusion: 30 minutes

Observation period post-infusion: none

Standard of Care (SOC) Dosing of Belatacept:

5 x the patient's weight (in kg) = mg of Belatacept. Dose then needs to be rounded to the nearest 12.5 mg increment. Example: 74 kg patient x 5 = 370 mg; rounded to the nearest 12.5 mg increment = 375 mg. At the end of 12 months, study subjects have completed the study drug protocol and they have the option to continue on Belatacept treatment, paid for by their medical insurance, or they can switch back to a CNI.

**Please see additional important study drug information on pages 11-12.

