9.1 Site Labs - See SOE, on page 19, for complete labs schedule

Blood Pressure - sitting

Urinalysis with sediment

Urine: protein, Urine: creatinine on spot sample; Urine protein/creatinine ratio (calculation)

Serum Creatinine

9.2 Central Labs: Mechanistics (See SOE, on page 19, for complete Central Labs schedule)

9.2.1 Anti-HLA antibody: recipient's serum will be tested for the presence of anti-HLA antibodies through Luminex single antigen bead assay. In this assay, patient's serum is incubated with microbeads coated with purified HLA proteins and then a fluorescent anti-IgG is used for antibody detection. Mean fluorescence intensity and donor-specificity of the antibodies present will be determined by correlating with known HLA antigens from donor.

9.2.2 Urine B7-1 quantitative: we will isolate RNA from urinary extracellular vesicles (EVs) of transplanted patients and detect B7-1 mRNA using "Droplet Digital" PCR system.

9.2.3 B7-1 biopsy staining: Using a goat anti-human B7-1 (CD80) antibody, we will perform immunostaining for B7-1 on frozen sections of allograft biopsies.

10. Safety and Reporting:

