Study Visits	Screening	Day 1 60 days	Day 15 + 5 days	Day 29 M 1 + 5 days	Day 43 M 2 + 5 days	Day 57 M 3 + 5 days	Day 85 M 4 + 5 days	Day 113 M 5 + 5 days	Day 141 M 6 + 5 days	Day 169 M 7 + 5 days	Day 197 M 8 + 5 days	Day 225 M 9 + 5 days	Day 253 M 10 + 5 days	Day 281 M 11 + 5 days	Day 309 M 12 + 5 days	Day 337 M 13 + 5 days	M18 + 5 days	
Procedures																		
Full Medical History	X																	
Physical Exam	X																	
Vital Signs^a	X	X	X	X	X	X	X	X	X	X	X	X	X	X	X	X		
Chart Review Only																X	X ^f	
Serum or Urine Pregnancy Test (WOCBP only*)	X*																	
EBV Serology^a	X																	
Spot Urine Protein/ Creatinine Ratio^a	X			X			X			X			X			X		
Urine^{a,b}	X			X			X			X			X			X		
Cholesterol Panel^a	X															X		
Serum Glucose^a	X			X			X			X			X			X		
Serum Creatinine^a	X			X			X			X			X			X		
anti-HLA Antibody^c	X ^a															X		
B7-1 biopsy staining^c	X																	
Research Urine^c	X															X		
Research Blood^c	X															X		
Belatacept Infusions^a		X	X	X	X	X	X	X	X	X	X	X	X	X	X	X		
CNI Taper		X ^d	X ^d	X ^e														
AE/SAE Reporting		X	X	X	X	X	X	X	X	X	X	X	X	X	X	X		

KEY:

^aStandard of Care (SOC)

^bUrine = urinalysis w/sediment **AND** Spot Urine = Urine:Creatinine & Urine:Protein; **AND** Urine Protein/Creatinine ratio = calculation needed

^cCentral Lab = send to BWH (transplant research center, [name])

^dCNI dosing to be tapered 25% of baseline dose **PER WEEK** (weekly reduction NOT represented on this SOE), dates of reduction must be documented in eCRFs.

^eLast day of CNI; CNI completely stopped after this day.

^fCollect information about last blood pressure, medications, serum creatinine and urine protein/creatinine

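### No graft-function test is scheduled for 56 days after the last CNI day (Day 29 to Day 85), and the protocol does not say why this switch is followed more lightly than the one in Section 9B

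*Combined protocol and SAP*

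**What the plan says.** **The trial's own switch.** Section 8 starts belatacept on Day 1 with further infusions on Days 15, 29, 43 and 57, then every 28 days. The CNI stays at full dose for week 1 and is then "tapered by 25% each week and discontinued at the end of week 4 (day 29"). SOE footnote e confirms Day 29 as the last CNI day.

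**Scheduled tests.** Section 9.1 lists blood pressure, urinalysis, urine protein/creatinine and serum creatinine as site labs and defers to the SOE for timing: "See SOE, on page 19, for complete labs schedule". The SOE row "Serum Creatinine^a" is marked at Screening and Days 29, 85, 169, 253 and 337. Urinalysis and spot urine protein/creatinine are marked at the same visits. Days 43 and 57 carry vital signs, infusion and AE/SAE reporting only. Footnote a labels creatinine as standard of care.

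**The switch off belatacept.** Section 9B begins: "Subjects in whom Belatacept dosing is discontinued should be placed on a conventional immunosuppressive regimen". It then gives its reason, "To ensure the safety of immunosuppression conversion", and requires that "repeated blood work for creatinine and drug levels will be performed a 1 week, 2 weeks and 4 weeks post-conversion", with a clinic visit at one month.

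**The risk.** Section 8.1.1: "Acute rejection is expected to be the principle risk in this study".

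**The concern.** Section 9B recognises that a change of immunosuppression calls for early, repeated creatinine checks. The SOE has none in the eight weeks that start when the CNI is withdrawn, although this is the switch under study and the protocol expects rejection to be its main hazard.

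The SOE plans no follow-up biopsy (its only biopsy item is B7-1 staining at Screening), and the protocol states no trigger for a for-cause biopsy. Scheduled creatinine and urine tests are therefore the only planned laboratory signals of graft function.

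Three parts of the plan depend on timely detection:

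- the secondary endpoint of acute rejection episodes;
- the individual stopping rule for refractory, biopsy-confirmed cellular rejection (Section 9C);
- the rule that interrupts the trial if PTLD or refractory rejection develops in two or more subjects (also 9C).

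If detection in this interval rests on tests that each clinic chooses to order, ascertainment may differ among the three sites. For a trial whose stated purpose is safety, that matters more than it would in an efficacy trial.

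**Working it through.** No sample-size or power calculation is involved. The check maps the SOE rows to their visit columns and counts days.

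**1. Visit days.** Section 8 gives Days 1, 15, 29, 43 and 57, then every 28 days: 57 + 28 = 85. This reproduces the SOE visit days. The SOE month labels do not track the day counts (Day 85 is labelled M 4), so I use days throughout.

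**2. Creatinine draws.** Screening and Days 29, 85, 169, 253 and 337. Blank at Days 1, 15, 43 and 57. The first on-treatment draw is in the column headed "Day 29 M 1 + 5 days".

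**3. Interval after the last CNI day.**

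- Nominal: 85 − 29 = 56 days = 8.0 weeks.
- Shortest, with the Day 29 visit 5 days late: 85 − 34 = 51 days.
- Longest, with the Day 85 visit 5 days late: 90 − 29 = 61 days.

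**4. Other intervals.**

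- Later draws are 84 days apart (169 − 85 = 84; 253 − 169 = 84; 337 − 253 = 84).
- Before Day 29 the only value is from Screening, so nothing is scheduled during the taper until its last day. How old the Screening value is depends on how the 60-day entry in the Day 1 column is read; the conclusion does not use it.

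**5. The 9B time points placed on the CNI-to-belatacept switch.** Conversion could be dated from the last CNI day or from the first infusion, so both are shown.

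| Conversion dated from | +1 week | +2 weeks | +4 weeks | SOE draws on these days |
|---|---|---|---|---|
| Day 29 (last CNI day) | Day 36 | Day 43 | Day 57 | 0 of 3 |
| Day 1 (first infusion) | Day 8 | Day 15 | Day 29 | 1 of 3 (Day 29) |

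Days 15, 43 and 57 are existing infusion visits. Days 8 and 36 are not SOE visits.

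**6. Search for draws elsewhere.** No other section adds a creatinine after CNI withdrawal. SOE footnote f, for the 18-month chart review, asks for the latest values only, so it would not recover results from Days 29 to 85.

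**The case against.** **Section 9B covers a different group.** It is written for subjects who stop belatacept. Its drug levels suit a restarted conventional drug, and those subjects no longer have infusion visits. This stands. A reader might infer that 9B sets a monitoring standard for any switch and that the SOE violates it. The text does not support that: the two passages apply to different subjects and do not formally conflict. What remains is that a safety reason stated in general terms is acted on for one switch and not for the other, without explanation.

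**Conversion may run from Day 1.** The protocol uses the word for the start of belatacept dosing. The Day 29 draw then meets the four-week point and already follows several weeks of CNI reduction. This also stands, and it is why both counts are given. It does not shorten the 56 days that follow.

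**Subjects are still seen.** Vital signs and AE/SAE reporting are scheduled at Days 43 and 57, and clinics may draw creatinine as standard of care. A reader might infer that rejection would go unseen for eight weeks, or that harm to subjects is established. Neither follows, since symptomatic rejection could surface by these routes. But the protocol neither requires such tests in this interval nor asks for their results to be recorded. The Manual of Procedures, to which it defers eCRF matters, is not among the documents.

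**The endpoint is descriptive.** Acute rejection is only summarised, and no between-site comparison is planned. That limits the statistical consequence, though a descriptive rate still depends on how cases are found.

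**The rejection figure cannot size the gap.** Section 8.1.1 gives an incremental rejection risk of up to 10%. A reader might multiply this by 36 subjects. The figure has no time frame, so the product would say nothing about rejection between Days 29 and 85.

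**Conclusion.** The point holds as an unexplained gap in scheduled monitoring, not as a breach of Section 9B. After the last CNI day there are 56 days (51 to 61 with visit windows) without a protocol-scheduled creatinine, urinalysis or urine protein/creatinine, and none is scheduled between Screening and Day 29. The SOE matches 0 or 1 of the three 9B time points, depending on the date taken as conversion.

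This rests on two readings: that the SOE is the full lab schedule, as Section 9.1 states, and that Day 29 is the last CNI day, as Section 8 and footnote e agree. How many rejections would be found late cannot be estimated from the documents.

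Severity: should-fix. The main expected risk and a secondary endpoint are affected, but other routes of detection exist.

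**What to change.** 1. **Reconcile the SOE creatinine row with the safety rationale in Section 9B**, or state in the protocol why the two conversions are monitored differently. The frequency is for the sponsor to set. The existing infusion visits from Day 1 to Day 57 could carry any added draws without a new visit. Matching the one-week point of 9B exactly would need a visit that the SOE does not have (Day 8 or Day 36).

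2. **Record all standard-of-care creatinine values from Day 1 to Day 85, with dates, in the eCRF.** Whatever frequency is chosen, this shows how intensively each site tested and puts rejection ascertainment on a comparable basis across the three sites.

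**Cost:** a protocol and SOE amendment, plus a small laboratory and data-entry burden. If the sponsor keeps the present schedule and justifies it, only the explanatory text and the data field are needed.
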